#### **Specific Aim 2: Determine the effect of the early use of the OWSV on the quality of speech.**

Hypothesis 2a: The increase in the speech intelligibility scores from pre- to post- assessment will be significantly higher in the patients who receive early OWSV compared to those who receive it the traditional way 48 hours after undergoing a tracheostomy.

Research Question 2b: Is the duration of speech longer for patients who start using OWSV earlier compared to those who start late?

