#### **Specific Aim 3: Determine the effect of early use of the OWSV on clinical outcomes.**

Hypothesis 3a: The increase in the health-related quality of life scores from pre- to post- assessment will be significantly higher in the patients who receive early OWSV compared to those who receive it the traditional way 48 hours after undergoing a tracheostomy.

Hypothesis 3b: There will be no significant changes in the rate of complications between patients receiving early versus standard use of the OWSV.

Hypothesis 3c: Patients who begin to use the OWSV early will have a significantly shorter lengths of stay in the ICU than patients who start using OWSV after 48 hours.

**3. Background** (briefly describe pre-clinical and clinical data, current experience with procedures, drug or device, and any other relevant information to justify the research)

Current standard of care to wait 48 hours following tracheostomy procedure to initiate OWSV assessment and treatment, however, there is scant evidence in the literature justifying this amount of time. 201 patients out 272 patients who received a tracheostomy received SLP consult for in 2014. Based on prior data from the tracheostomy database 30% of mechanically ventilated and / or tracheotomized patients tend to be awake and interactive, and attempt to communicate.

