**Sequence and timing:**

- A. Screening by Tracheostomy Nurse Practitioner following percutaneous tracheotomy
1. Glasgow Coma Scale (GCS)
  2. Richmond Agitation Sedation Scale (RASS)
- B. Speech-Language Pathologist consult is placed for patients meeting study inclusion criteria
- C. Patient consent is obtained by Tracheostomy Nurse Practitioner or Speech-Language Pathologist
- D. Randomization into Intervention and Control groups
- E. Session 1 within 12-24 hours following percutaneous tracheotomy:
1. Both groups complete pre-assessment consisting of the following:
    - i. Electronic Patient Records (POE, EPR, or EPIC)
      1. Demographic Data
      2. Patient Characteristics
      3. Sequential Organ Failure Assessment (SOFA)
    - ii. Confusion Assessment Method for the ICU (CAM-ICU)
    - iii. Health-related quality of life survey, Quality of Life – Mechanical Ventilation (QOL-MV)
    - iv. Tracheostomy-related assessment
      1. Trach size
      2. Mechanical ventilation status
      3. Secretions & tolerance of cuff deflation
      4. Presence of complications
        - i. Bleeding at stoma
        - ii. Subcutaneous air
        - iii. Infection at stomal site
        - iv. Pneumothorax
        - v. Accidental decannulation
  2. Intervention Group completes standard SLP evaluation and OWSV trial:
    - i. SLP evaluation includes the following to assess candidacy for OWSV trial:
      1. Level of alertness
      2. Cranial nerve exam
      3. Ability to cough
      4. Ability to tolerate cuff deflation
      5. Ability to tolerate finger occlusion
      6. Vocal quality
    - ii. If appropriate, OWSV will be trialed and assessed for the following:
      1. Duration of tolerance
      2. Change in vital signs
      3. Vocal quality
      4. Presence of air trapping
      5. Sentence Intelligibility Test
    - iii. Recommendations are made for OWSV use outside of SLP supervision
      1. Supervision requirement (RN, Respiratory therapist, trained family, independent)
      2. Duration of OWSV use
  3. Control Group receives no further evaluation or treatment during Session 1, which constitutes current standard of care.
- F. Session 2 within 48-60 hours following percutaneous tracheotomy:
1. Both groups complete post-assessment:

Date: 2/06/18

Principal Investigator: [name]

Application Number: IRB00080981

[figure not shown]
- i. Electronic Patient Records (POE, EPR, or EPIC)
    1. Demographic Data
    2. Patient Characteristics

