    3. Sequential Organ Failure Assessment (SOFA)
  - ii. Health-related quality of life survey (QOL-MV)
  - iii. Confusion Assessment Method for the ICU (CAM-ICU)
  - iv. Tracheostomy-related assessment
    1. Trach size
    2. Mechanical ventilation status
    3. Secretions & tolerance of cuff deflation
    4. Presence of complications
      - i. Bleeding at stoma
      - ii. Subcutaneous air
      - iii. Infection at stomal site
      - iv. Pneumothorax
      - v. Accidental decannulation
  2. Intervention Group completes second SLP evaluation and OWSV trial.
  3. Control Group completes initial SLP evaluation and OWSV trial.
- G. Session 3 following first trach change
1. Both groups receive follow-up SLP re-evaluation and OWSV trials as appropriate per standard of care.

**Setting:** All ICUs at the Johns Hopkins Hospital

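### H2a compares pre-to-post gains in speech intelligibility between arms, but the schedule gives controls no pre score and the planned paired t-test is not a between-arm test

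*Combined protocol and SAP*

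**What the plan says.** Section 7a makes speech intelligibility the primary outcome. In Section 2, Specific Aim 2, H2a is the only hypothesis about it: "The increase in the speech intelligibility scores from pre- to post- assessment will be significantly higher in the patients who receive early OWSV", the comparator being patients who start at 48 hours.

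Section 4a, Sequence and timing, fixes what is measured and when:

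- **E.1 (Session 1, 12 to 24 hours, both arms):** "Both groups complete pre-assessment consisting of the following". The list holds record data with SOFA, CAM-ICU, the QOL-MV and a tracheostomy-related assessment. The SIT is not in it.
- **E.2 (Session 1, intervention arm only):** a speech-language pathologist (SLP) evaluation, then a valve trial introduced by "If appropriate, OWSV will be trialed and assessed for the following". The SIT is the fifth item there. The schedule names it nowhere else.
- **E.3 (Session 1, controls):** "Control Group receives no further evaluation or treatment during Session 1, which constitutes current standard of care".
- **F.1 (Session 2, 48 to 60 hours, both arms):** the same four components as E.1, again without the SIT.
- **F.2 and F.3 (Session 2):** "Intervention Group completes second SLP evaluation and OWSV trial"; "Control Group completes initial SLP evaluation and OWSV trial".
- **G (Session 3, after the first tube change):** further evaluation and valve trials in both arms where suitable.

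The Instruments table lists the SIT (11 items) without timing or arm. For continuous scores, Section 7c plans paired t-tests of pre against post and names no between-arm test.

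**The concern.** A difference between arms in pre-to-post increase needs a pre and a post score in each arm. The schedule supplies no control pre score, and its only named intervention score at Session 1 is obtained with the valve in use, in patients judged suitable for it. The parallel quality-of-life hypothesis, H3a, shows what a complete schedule looks like: it concerns "The increase in the health-related quality of life scores from pre- to post- assessment", and its instrument is listed for both arms in E.1 and again in F.1. The gap is specific to the primary outcome.

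If it stays, the team must either settle on a control pre value after the data are in or change the hypothesis at that stage. A Session 1 score that was not taken cannot be recovered later.

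**Working it through.** **Denominator.** Section 7c starts from about 55 eligible patients and allows 10% for refusal: 55 × (1 − 0.10) = 49.5, rounded to 50, or 25 per arm. The plan's figure reproduces.

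**Where a SIT is scheduled (Section 4a):**

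| Session | Intervention | Control |
|---|---|---|
| 1 (12–24 h) | Named in E.2, conditional, during the first valve trial | None: absent from E.1, and E.3 adds nothing |
| 2 (48–60 h) | Implied by F.2 | Implied by F.3, first control SIT |
| 3 | Implied by G, where suitable | Implied by G, where suitable |

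Of the six cells, one is named, four are implied and one is empty. The implied entries assume that a valve trial at Sessions 2 and 3 has the content given in E.2.

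**Change scores, Session 1 to Session 2.** Controls: 0 of 25. Intervention: at most 25 of 25. So at most 25 of 50 patients have a change score, all in one arm. H2a is (mean change, intervention) − (mean change, control). The second term is a mean over no patients, so the contrast is undefined.

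**What the intervention arm's change would measure.** Its Session 1 SIT is taken with the valve in use. The change to Session 2 runs from first valve use to a later use and leaves out any gain on first use, which is not the increase that H2a describes.

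**Other sources of a control pre score:**

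- Session 2 is labelled the post-assessment, so it cannot also be pre.
- Session 3 comes after the post-assessment.
- No section assigns controls a baseline value such as zero.
- The Instruments table gives no timing.
- Section 9a mentions SLP time during the pre- and post-assessments but schedules no test.

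**The test.** A paired t-test asks whether the mean change within a set of patients is zero. Run in one arm, or in both arms pooled, it does not estimate the difference between arms. In controls it could not be run on the SIT at all.

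**Is a baseline needed?** Let B be the expected no-valve score, the same in both arms by randomisation, and let Y1 and Y0 be the expected Session 2 scores in the intervention and control arms. Then (Y1 − B) − (Y0 − B) = Y1 − Y0. The expected difference in increase equals the expected difference at Session 2, so a Session 2 comparison addresses the same contrast without a baseline.

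**The case against.** The strongest reply is that this is a missing definition more than lost data. The abstract describes patients without a voice whose speech the valve restores, so a no-valve score near zero is plausible and the increase would then be the Session 2 score. Arms are randomised and Session 2 SITs are implied in both. This stands as an argument for the simpler repair. It does not rescue the text, which states no baseline value and still words H2a as a change.

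A second reply is that the codebook cited in Section 7b may place a SIT in the pre-assessment. It is not among the documents. If it does so, E.1 and E.3 conflict with it and need correcting.

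A third is that adding a baseline SIT is not free. Section 8a notes the burden of repeated questionnaires, and a no-valve test could give controls part of the evaluation that E.3 withholds. This stands in part: tolerance of cuff deflation is already assessed in both arms under E.1, but finger occlusion appears only in E.2. The no-valve condition must therefore be defined with care.

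A fourth is that this is a pilot whose abstract puts safety first. That is true, but the protocol itself makes intelligibility primary and attaches a directional between-arm hypothesis to it.

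A reader might also infer that the gap would reverse the sign of a real benefit, for example if the valve-on score served as pre in the early arm and an assumed no-voice value in controls. The documents propose no such substitution and give no figure for the gain on first use, so neither the size nor the direction of a bias can be claimed.

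**Conclusion.** The concern holds on the text. With the stated schedule and test, the primary hypothesis cannot be answered: 0 of 25 controls have a pre score, the intervention arm's Session 1 score is conditional and not an untreated baseline, and the planned test is within-arm. The likeliest explanation is a drafting omission from E.1.

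It would go too far to infer that the trial yields no usable comparison of intelligibility. A randomised Session 2 comparison remains available. That rests on two assumptions: that F.2 and F.3 include the SIT, and that patients who are removed or cannot be scored are handled by a rule set in advance, which is a separate matter. Nor does the missing measurement extend to quality of life or complications, which are scheduled in both arms at both sessions.

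**What to change.** Choose one of two routes.

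**(a) Least burdensome.** Restate H2a as the between-arm difference in Session 2 SIT. Name the SIT in F.1 for both arms, under one stated valve condition. For any patient already past Session 1, this is the only route open.

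**(b) Keep H2a as a change hypothesis.** Add a SIT to E.1 for both arms, before any valve trial, under one defined no-valve condition that does not give controls the parts of the SLP evaluation reserved for E.2. Reconcile E.3 with it, and name the SIT in F.1 as in (a).

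Under neither route should the valve-on Session 1 score serve as pre.

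In Section 7c, replace the paired t-test for H2a with one pre-specified comparison by assigned arm, with a 95% confidence interval: Session 2 SIT under (a), or Session 2 SIT adjusted for the E.1 SIT under (b). Fix the parametric or rank-based form in advance, not from the number of zeros observed.

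**Cost.** A protocol amendment and no new visit. Route (a) adds no test beyond those already implied. Route (b) adds at most one 11-item test per patient (50 × 1 = 50 in all). Under either route the early arm repeats the valve-on SIT at Session 2 while controls take it for the first time, so familiarity with the test may contribute to the difference. State this as a limitation.

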## 7. Study Statistics

- a. Primary outcome variable.

Speech intelligibility

- b. Secondary outcome variables.

- Patient characteristics
- Quality of Life
- Complications
- Time to events
- Length of stay
- Mortality

\*See codebook for list of additional variables

- c. Statistical plan including sample size justification and interim data analysis.

Mean, standard deviation, median and inter-quartile range will be calculated for continuous variables. Paired t-tests will be used to compare pre and post assessment scores for continuous variables. Frequencies and percentages will be calculated for categorical variables. Chi square and Fisher Exact tests will be used to compare pre and post assessment scores of categorical variables. Sample size is estimated based on 30% of tracheostomy patients who might be awake and interactive at the Johns Hopkins Hospital in 2016, as per the tracheostomy database. According to the 2014 data, we found that about 55 patients were awake and interactive while having a percutaneous tracheostomy tube at the hospital. Considering a 10% of the patients who may not be interested in the study, we will plan for a sample size of 50 with 25 in the intervention group and 25 in the control group.

- d. Early stopping rules.

If patients have changes in clinical condition that prevents cuff deflation, they will be dropped from the study. The study will be halted if any major complications occur from early trial of OWSV.

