## 8. Risks

- a. Medical risks, listing all procedures, their major and minor risks and expected frequency.  
Risks of OWSV use include development of subcutaneous air and air trapping that could lead to respiratory distress.

Administration of questionnaires repeatedly can be burdensome. In addition, questions about their quality of life while mechanically ventilated may be emotionally distressing.

- b. Steps taken to minimize the risks.

Patients will be screened by the tracheostomy nurse practitioner for inclusion in the study, and all patients enrolled in the study will undergo thorough evaluation with an SLP per standard protocol, prior to the trial with the OWSV. Trial of the OWSV will be deferred if the SLP determines that the patient is not an appropriate candidate to trial the OWSV at the time. The SLP will follow standard protocol during OWSV trials of appropriate candidates. OWSV trials will be discontinued and SLP will refer to the medical team if the patient experiences any complications.

During administration of questionnaires, the interviewer will stop the interview and refer to the medical team providing care in the ICU if at any time the participant appears upset or distressed. The interviewer will remain with the participant until she or he has regained emotional equilibrium. If the participant states that he/she is tired and would like to rest, the interviewer will stop the interview and come back at a later time to continue with the interview. The participant may wish to withdraw from the study anytime they choose to.

- c. Plan for reporting unanticipated problems or study deviations.

The PI will discuss any unanticipated problems of study deviations that pertain to the participants' health with the medical team caring for the patient.

Date: 2/06/18

Principal Investigator: [name]

Application Number: **IRB00080981**

- d. Legal risks such as the risks that would be associated with breach of confidentiality.  
Data will be stored in RedCap database that is password protected on the ICTR server. The database can only be accessed by the study team and the PI. Upon, completion of data collection, names and medical record numbers will be removed. A new research ID number will be assigned for analysis. Any document that may re-identify the patient will be destroyed. Once the data are de-identified, then analysis will begin.
- e. Financial risks to the participants.  
N/A

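### The plan gives no between-arm analysis for the complication hypothesis (H3b) and no rule separating new complications from those already present before any valve use

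*Combined protocol and SAP*

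**What the plan says.** Under Sequence and timing, Session 1 (12 to 24 hours after the procedure) opens with an assessment in both arms: "Both groups complete pre-assessment consisting of the following". It includes a tracheostomy item, "Presence of complications", covering stomal bleeding, subcutaneous air, stomal infection, pneumothorax and accidental decannulation. The intervention arm's first valve trial is the next step. The same five-item list is repeated in both arms in the post-assessment of the second visit ("Session 2 within 48-60 hours following percutaneous tracheotomy"). For controls, the first valve trial is listed after that post-assessment: "Control Group completes initial SLP evaluation and OWSV trial".

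Hypothesis 3b reads: "There will be no significant changes in the rate of complications between patients receiving early versus standard use of the OWSV". No margin is given. Section 7 names complications as a secondary outcome, and the only method it states for categorical data is: "Chi square and Fisher Exact tests will be used to compare pre and post assessment scores of categorical variables". It also points to a codebook for further variables: "See codebook for list of additional variables".

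Section 8 describes the valve's own risks: "Risks of OWSV use include development of subcutaneous air and air trapping that could lead to respiratory distress". Subcutaneous air is on the five-item list. Air trapping is not; it is listed only among the observations made during a valve trial.

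**The concern.** H3b asks whether the two randomised arms differ. A test of Session 1 against Session 2 scores answers another question, and no between-arm test for complications is given. Whoever analyses the trial must therefore choose one.

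The readiest choice is to compare the proportions with a complication at Session 2. That count would mix two kinds of event: complications of the tracheostomy that were there before any valve was fitted, and complications that arose afterwards. Only the second kind can reflect valve timing. The first kind should be about equally common in both arms under randomisation, so it raises both proportions and brings their ratio closer to 1.

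The direction matters because H3b is framed so that a non-significant result supports it. Anything that blurs the contrast favours the conclusion that early use is safe.

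**Working it through.** **Sample size.** Section 7 takes about 55 eligible patients and allows 10% for refusal: 55 × 0.90 = 49.5, rounded to 50, or 25 per arm. This reproduces. It is a feasibility figure; the plan gives no complication rate, alpha or power.

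**Assumptions (none is in the documents).** Risk of a new complication between sessions is 4% with standard timing and 20% with early use. A proportion q of patients in each arm has a complication at Session 1 that persists to Session 2. The test is two-sided Fisher at 0.05, with power obtained by exact enumeration of two binomials with n = 25.

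**Three ways to count.**

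- A. Session 2 presence: q + (1 − q) × new-event risk.
- B. New events only in patients with no complication at Session 1, all 25 in the denominator: (1 − q) × new-event risk.
- C. New events in all patients, those with a Session 1 complication having the same new-event risk: 4% v 20% whatever q is.

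For q = 10%:

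- A: 0.10 + 0.90 × 0.04 = 13.6%, and 0.10 + 0.90 × 0.20 = 28.0%. Ratio 28.0 / 13.6 = 2.06; difference 14.4 points.
- B: 0.90 × 0.04 = 3.6%, and 0.90 × 0.20 = 18.0%. Ratio 5.0; difference 14.4 points.
- C: 4% and 20%. Ratio 5.0; difference 16.0 points.

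| q | A: presence | A: ratio | A: power | B: power | C: power |
|---|---|---|---|---|---|
| 0% | 4.0% v 20.0% | 5.0 | 23.0% | 23.0% | 23.0% |
| 5% | 8.8% v 24.0% | 2.7 | 19.2% | 20.2% | 23.0% |
| 10% | 13.6% v 28.0% | 2.1 | 14.7% | 17.5% | 23.0% |
| 20% | 23.2% v 36.0% | 1.6 | 9.8% | 12.4% | 23.0% |

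The ratio is badly distorted under A. The risk difference is the same under A and B, and smaller under A than under C (14.4 v 16.0 points at q = 10%; 12.8 v 16.0 at q = 20%). The power lost by using A at q = 10% is 17.5 − 14.7 = 2.8 points against B and 23.0 − 14.7 = 8.3 points against C.

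**A larger assumed effect.** With new-event risks of 5% and 30% and q = 20%, presence is 24% v 44% (ratio 1.83, power 22.8%), against 4% v 24% under B (ratio 6.0, power 38.0%). If only half of that 20% persists, presence is 14% v 34% (ratio 2.43, power 26.1%).

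**The case against.** A reader might infer that the plan counts old complications in both arms. The documents do not say so. No section makes raw Session 2 presence the H3b endpoint. The same list is taken before and after in both arms, and the stated test is pre versus post, which takes some account of baseline. This stands: comparison A is one way of filling a gap, not the stated analysis. The pre-versus-post test still does not compare the arms, and a persisting complication is simply positive at both visits.

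The size is also open to challenge. Baseline prevalence and persistence are assumed. Entry already excludes bleeding that needs transfusion or packing, and accidental decannulation is an event rather than a lasting state. The five items are pooled here although the plan does not pool them; item by item, dilution is probably smaller. All of this stands and limits the size, not the direction.

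A reader might further infer that dilution is why a non-significant H3b would tell us little. It is not the main reason: with no baseline complications at all, power is only 23.0% under the 4% v 20% assumption.

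Finally, the codebook was not available and may define the variable. That limits certainty that no rule exists anywhere, but the protocol text contains none.

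**Conclusion.** The point holds as a gap in outcome definition and analysis rule, not in data collection. As written, the plan yields no between-arm comparison for H3b and does not separate new from persisting complications, although the two planned assessments allow both.

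If Session 2 presence were used to fill the gap, the bias would run towards H3b's predicted result. Under the assumptions shown (4% v 20% new events, 10% persisting), the ratio falls from 5.0 to 2.1 and power is 14.7% instead of 17.5% to 23.0%, depending on whether patients with a baseline complication can still count. The effect on power is modest, the risk difference changes little or not at all, and everything vanishes if baseline prevalence is zero.

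**What to change.** In Section 7, define the H3b outcome per patient as at least one listed complication that is absent at Session 1 and present at Session 2. Compare it between the arms as randomised, as a risk difference with an exact 95% confidence interval, so that the reader sees how large an excess remains compatible with the data. Report Session 1 complications by arm as a baseline characteristic.

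Do not extend the definition to worsening: the listed items record presence only, with no severity grade, so worsening cannot be derived from them.

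Report air trapping separately, per valve trial performed. By the end of Session 2 the early arm is scheduled for two trials and the control arm for one, so adding it to the compared count would give the early arm more chances of detection.

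The H3b change costs analysis-plan wording only, since both assessments are already planned. For air trapping, confirm that the item listed for the Session 1 trial is also recorded at the Session 2 trials. There is one small downside: a further event of the same type in a patient who already had it at Session 1 is not counted. A complication that starts and resolves between sessions may also still be missed, as it may be under the present item.

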## 6. Drugs/ Substances/ Devices

- a. The rationale for choosing the drug and dose or for choosing the device to be used.

We are not studying the efficacy of the one-way speaking valves. We know that they work. We are studying the timing of when to start using OWSV.

- b. Justification and safety information if FDA approved drugs will be administered for non-FDA approved indications or if doses or routes of administration or participant populations are changed.

N/A

Date: 2/06/18

Principal Investigator: [name]

Application Number: **IRB00080981**

- c. Justification and safety information if non-FDA approved drugs without an IND will be administered.

N/A

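### H3a's last QOL-MV is scheduled before controls have used the valve, so it measures the short-term effect of an early offer, not whether any benefit persists once both arms have the valve

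*Combined protocol and SAP*

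**What the plan says.** Under Specific Aim 3, H3a predicts that quality-of-life scores will rise more between the two assessments in the early arm, "compared to those who receive it the traditional way 48 hours after undergoing a tracheostomy". Section 6a, on the choice of device, says "We are not studying the efficacy of the one-way speaking valves" and that the subject of study is when to start using it.

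The visit schedule is in Section 4a, under the heading "Sequence and timing":

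- **Session 1, 12–24 h after tracheotomy.** Both arms complete the pre-assessment, including QOL-MV (E.1.iii). The intervention arm then has the SLP evaluation and, if suitable, a valve trial, followed by recommendations for use outside SLP supervision (E.2). Controls receive nothing further (E.3).
- **Session 2, 48–60 h.** Both arms complete the post-assessment, including QOL-MV (F.1.ii). The intervention arm then has its second evaluation and trial (F.2). Item F.3 reads "Control Group completes initial SLP evaluation and OWSV trial".
- **Session 3, after the first tube change.** The only item is "Both groups receive follow-up SLP re-evaluation and OWSV trials as appropriate per standard of care".

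Section 4b puts participation at about 4 weeks with 3 visits. The Instruments table gives QOL-MV 12 items and describes it as a questionnaire for mechanically ventilated patients.

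**The concern.** H3a describes the comparator as patients who receive the valve at 48 hours. At the last scheduled QOL-MV, on the listed order, no control has yet received it. The post measure therefore captures the end of the standard wait and nothing after it.

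The risk lies in how a result would be reported. A higher QOL-MV gain in the intervention arm could arise simply because those patients could speak during the wait and controls could not, with the gap closing as soon as controls get the valve. Under H3a's present wording, that result would read as a general advantage of early over standard timing. The schedule has no QOL-MV that could separate a benefit confined to the first two days from one that persists, although a third visit is already planned.

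**Working it through.** **Plan's own figure.** Section 7c derives the sample size from feasibility: 55 × (1 − 0.10) = 49.5, rounded up to 50, or 25 per arm. This reproduces. Section 7c gives no alpha, power, effect size or SD, so the point cannot be checked as a power calculation. It concerns the schedule, and the check compares the QOL-MV times with first valve use in each arm.

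**Valve exposure at each scheduled QOL-MV**

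| | Intervention arm | Control arm |
|---|---|---|
| Session 1 QOL-MV (12–24 h) | none; the trial is listed after the pre-assessment | none |
| Session 2 QOL-MV (48–60 h) | first use at Session 1, if the trial was suitable | none, on the listed order (F.1 before F.3) |
| Session 3 | no QOL-MV listed | no QOL-MV listed |

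**Time since first valve use at the last QOL-MV, for an intervention patient who passed the Session 1 trial**

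- Shortest: latest Session 1 to earliest Session 2 = 48 − 24 = 24 h.
- Longest: earliest Session 1 to latest Session 2 = 60 − 12 = 48 h.

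This is elapsed time, not hours of wear. For a control it is 0 h.

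**Sensitivity to the order within Session 2.** No sentence states outright that the post-assessment precedes the control trial; that follows from the numbering under a heading about sequence. If the order were reversed, a control would have had at most one trial in the same session before answering. There would still be no QOL-MV after a period of valve use in the control arm.

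**Sensitivity to uptake.** The Session 1 trial takes place only if the SLP finds the patient suitable, and Section 8b allows deferral. The contrast is therefore early offer against no offer yet, not valve use against no use.

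**A related inconsistency.** Section 4d puts the intervention arm's head start at 24–60 hours, while the session windows give 24–48 hours. These passages must be reconciled.

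**The case against.** The strongest reply is that the Session 2 contrast is itself an effect of timing. One arm starts at 12–24 h and the other at 48–60 h, and the outcome at the end of the wait shows directly what the wait costs. The Abstract speaks of the consequences of delay, and Section 9 gives the prospective benefit as possibly regaining speech sooner. This stands. A reader might infer that H3a tests valve efficacy and not timing at all; the documents do not support that. Section 6a answers a form question on device rationale, and does not claim that the quality-of-life effect in the first 48–60 h is known. What remains is that the short-term effect is the only quality-of-life effect the schedule can estimate, while H3a is worded without that limit.

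Other stronger readings also fail:

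- **Session 3 collects no outcome at all.** Its valve trials may well carry the measures listed for a trial at E.2.ii, including tolerance duration and sentence intelligibility. QOL-MV and the complication checklist are what the Session 3 list lacks.
- **Research Question 2b has the same fault.** It asks "Is the duration of speech longer for patients who start using OWSV earlier compared to those who start late". A built-in advantage arises only if duration is a running total up to Session 2, and the documents never define it so. The duration listed for a trial is per-trial tolerance, and both arms have a trial at Session 2.
- **Nothing after catch-up can be answered.** ICU length of stay (H3c), mortality and time to events are not tied to Session 2. The gap is in quality of life.
- **A high probability of a misleading positive result can be quoted.** With 25 per arm and two-sided 0.05, Φ(d/√(2/25) − 1.96) gives about 18%, 42% and 81% for assumed effects of 0.3, 0.5 and 0.8 SD. No effect size or SD in the documents selects among these. All assume full uptake, no removals and a between-arm test, whereas Section 7c names only paired pre/post tests for continuous scores. None should be quoted as the size of the problem.

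Finally, resting H3a on Session 3 would exchange a fixed-window randomized comparison for one at an undated visit, after removals for discharge or clinical change (Section 4f). That objection is sound and shapes the fix.

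**Conclusion.** The point holds as a limit on what H3a can conclude. As scheduled, it estimates the effect on QOL-MV at 48–60 h of having the valve offered early against not yet offered. It cannot show whether early start still improves quality of life once both arms have used the valve.

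The size is best stated as the exposure gap at the last measurement: 24 to 48 h since first valve use for intervention patients who passed the Session 1 trial, against 0 h for controls (at most one same-session trial if the order is reversed). The conclusion rests on the visit schedule as listed. Section 7b cites a codebook that is not among the documents, so a later QOL-MV cannot be wholly excluded, but none is scheduled. Since quality of life is a secondary outcome in a pilot, this is worth correcting but does not undermine the design.

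**What to change.** 1. **Keep Session 2 as the H3a analysis.** Specify in Section 7c a between-arm comparison of Session 2 QOL-MV, adjusted for Session 1 QOL-MV. The paired tests now named do not compare arms.
2. **Limit the conclusion.** State in H3a and in reporting that the contrast is early valve offered versus not yet offered at 48–60 h.
3. **Fix the order in words.** Say explicitly whether the Session 2 QOL-MV is taken before the control arm's trial.
4. **Add QOL-MV and the complication checklist at Session 3 in both arms,** and record time since tracheostomy. Report the between-arm Session 3 QOL-MV difference, adjusted for Session 1 QOL-MV, as a supporting analysis of persistence, not as a replacement for H3a. Report by arm how many patients reach the visit and how many are still ventilated.

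The cost is protocol wording plus one 12-item questionnaire and a short checklist at a visit already planned; no treatment changes. The downsides should be named in the plan. Section 8a already recognizes that repeated questionnaires are a burden. Session 3 has no fixed date, discharged or removed patients will be missing, and some patients will no longer be ventilated when an instrument designed for ventilated patients is given. Those limits are why the Session 3 result should be supporting only.
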